### Analysis Populations

The primary endpoint will be analyzed using the data sets as defined below:

1. Intention to Treat (ITT) analysis population will include all subjects who signed informed consent and for whom the study procedure was initiated.
2. Per Protocol (PP) analysis population will include all subjects who met all eligibility criteria, signed informed consent, and for whom the procedure was completed as

specified in section 9 without deviation. The PP analysis population is a subset of the ITT population. If there are no differences in the ITT and PP analysis populations, separate analyses will not be presented.

The determination of any subjects excluded from the PP analysis population will be made prior to locking the study database for final analysis. All safety summaries will be based on the ITT analysis population.

### **Handling of Missing Data**

CRFs will be monitored for accuracy and missing data, and queries will be issued to the sites for resolution. Every attempt will be made to maximize the likelihood of obtaining data to support the study endpoint

The table below lists anticipated situations which may occur resulting in missing data for the primary endpoint, and the steps that will be taken to minimize the occurrence.

**Table 3: Steps to Minimize Missing Data for the Primary Endpoint**

Source of missing data	Steps to minimize missing data
Unable to induce a ventricular arrhythmia	History of difficulty of ventricular arrhythmia induction has been specified in the exclusion criteria.
Unable to induce a ventricular arrhythmia with heart rate greater than 150 bpm	History of difficulty of ventricular arrhythmia induction has been specified in the exclusion criteria.
No induction attempted due to change in patient's hemodynamic status	Conditions which place the patient at perceived high risk have been specified in the exclusion criteria.
Rescue shock delivery before either a 1 st or 2 nd shock from the Test System	Protocol training will be provided for the investigator and EP staff.
Pacing or shock therapy from CIED delivered before either a 1 st or 2 nd shock from the Test System	

1. Protocol training will be provided for the investigator and EP staff.

2. Instruction to program CIED therapies OFF is specified in the EP procedure (Section 9).

Pacing from external EP system delivered before either a 1 st or 2 nd shock from the Test System	Protocol training will be provided for the investigator, EP staff and operators
No shock delivered from the Test System due to procedure setup or operator error	

1. Protocol training will be provided for the investigator, EP staff and operators.

2. Operators will be trained on the Test System.

No shock delivered from the Test System due to equipment failure	Each Test System must pass manufacturing test before shipment to the clinical site. In

	addition, the ASSURE WCD Monitor executes a self-test upon boot-up.
--	---

Occurrence of any of these situations shall be reviewed with the Sponsor and the Study PI prior to enrolling any additional subjects at that site. If there still are missing data despite efforts to minimize it the investigator will document on a CRF the reason/rationale for the missing data.

### **Primary Endpoint Analysis**

The primary endpoint analysis will be performed after all subjects have completed the study and the study database has been cleaned, verified and locked. The data from all clinical sites that participate in this study will be combined so that the target sample size will be available for analysis.

The primary endpoint will be calculated as the ratio of the number of subjects with successful (first or second shock) arrhythmia conversion using the Test System to the number of total inductions attempted with shocks delivered by the Test System in the respective data set. A successful arrhythmia conversion is defined as termination of an induced ventricular rhythm ( $\geq 150$  bpm) by first or second shock from the Test System to a non-shockable rhythm (rhythms other than VT or VF).

Performance criteria will be based on comparison to the published conversion efficacy point estimate of 94% reported for the ZOLL LifeVest (Wäßnig NK), which is the only comparable commercially-available device.

The Pass/Fail criteria will be based on the primary endpoint using the PP analysis population (See Table 3).

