**Table 4: Pass/Fail Criteria - Estimated Conversion Rate Based on Study Results**

Successful Conversion	Estimated Conversion Rate	95% Confidence Interval
20 out of 20	100.0%	(83.2%, 100.0%)
19 out of 20	95.0%	(75.1%, 99.9%)
≤ 18 out of 20	Failure to Meet Primary Endpoint	N/A
19 out of 19	100.0%	(82.4%, 100.0%)
18 out of 19	94.7%	(74.0%, 99.9%)
≤ 17 out of 19	Failure to Meet Primary Endpoint	N/A
18 out of 18	100.0%	(81.5%, 100.0%)
17 out of 18	94.4%	(72.7%, 99.9%)
≤ 16 out of 18	Failure to Meet Primary Endpoint	N/A
17 out of 17	100.0%	(80.5%, 100.0%)
16 out of 17	94.1%	(71.3%, 99.9%)
≤ 15 out of 17	Failure to Meet Primary Endpoint	N/A

Two analyses of the primary endpoint will be conducted, one using the PP data set and a second using the ITT data set. The ITT analysis will include all 20 subjects regardless of missing data. If there is missing data, a tipping point analysis (including best- and worst-case scenarios) will be used to assess sensitivity of the analysis to the missing data. The difference between the conversion rate estimates from the PP and ITT analyses will be used to assess the magnitude of missing data bias.

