  - If the arrhythmia is less than 150 bpm, convert the patient's arrhythmia using the backup rescue defibrillator and/or standard of care procedures.
  - Repeated induction attempts may be performed to induce the ventricular rhythm. The investigator may stop induction attempts at any point if in their judgement it is no longer in the best interest of the patient.
  - Conversion is defined as the presence of a non-shockable rhythm (rhythms other than VT or VF) after shock delivery
- 8. (Kestra Clinical Specialist under the direction of the Investigator or Sub-Investigator) If the Arrhythmia is estimated to be greater than 150 bpm, deliver a 170J shock from the Test System.
- 9. (Kestra Clinical Specialist under the direction of the Investigator or Sub-Investigator) Deliver a second shock at 170J from the Test System if the first shock is unsuccessful.
- 10. (Investigator or Sub-Investigator) If both attempts to convert using the Test System are unsuccessful, convert the patient's arrhythmia using the backup rescue defibrillator, implantable defibrillator and/or standard of care procedures.

Time to the first shock from the Test System will be approximately 6 seconds. Total time to an external rescue shock, if needed, is estimated to be approximately 20 seconds.

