**Figure 3: Time to shock**

11. (Kestra Clinical Specialist) After conversion of the arrhythmia, disconnect the Test System from the adhesive pads.

12. Obtain copies of procedure documentation

- Download the manual shock log from the tablet
- Electronic or paper record of the ECG signals from the EP monitoring system (from induction through conversion)
- Study-specific physician procedure report (de-identified)

The following situations are examples of protocol deviations:

- a) Rescue shock delivered before a first or second Test System shock delivered
- b) Therapy delivered from external EP system (e.g. ATP/pacing), or CIED (ATP/shock) before a first or second Test System shock delivered
- c) No shock delivered from Test System (equipment failure or operator error)
- d) No induction attempted after enrollment due to change in patient's hemodynamic status

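### Pass/Fail rests on the Per Protocol set, which drops a subject whom the Test System shocked but did not convert if other therapy came before the second shock; at PP n of 17 to 20 the verdict is then the same as if that subject had converted

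*Combined protocol and SAP*

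**What the plan says.** All references are to the combined protocol and SAP.

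- **Deciding set.** Section 7, Primary Endpoint Analysis: "The Pass/Fail criteria will be based on the primary endpoint using the PP analysis population". The sentence refers the reader to Table 3, but the criteria are in Table 4.
- **PP membership.** Section 7, Analysis Populations: the subject must be eligible and consented, with the procedure completed as "specified in section 9 without deviation". Exclusions are settled before database lock.
- **Deviations.** The examples at the end of the Electrophysiology (EP) Procedure in Section 9 include (a) "Rescue shock delivered before a first or second Test System shock delivered" and (b) "Therapy delivered from external EP system (e.g. ATP/pacing), or CIED (ATP/shock) before a first or second Test System shock delivered".
- **When a second shock is given.** Step 9 of that procedure: "Deliver a second shock at 170J from the Test System if the first shock is unsuccessful".
- **The ratio.** The denominator is the "number of total inductions attempted with shocks delivered by the Test System in the respective data set". A success is termination of the induced ventricular rhythm "by first or second shock from the Test System to a non-shockable rhythm (rhythms other than VT or VF").
- **Same events as missing data.** Table 3 lists rescue, CIED and pacing therapy before a first or second Test System shock as sources of missing primary-endpoint data.
- **Supporting analyses.** After Table 4, an ITT analysis of all 20 subjects is planned and, if data are missing, "a tipping point analysis (including best- and worst-case scenarios) will be used to assess sensitivity of the analysis to the missing data". The PP–ITT difference is to be used to size missing-data bias. No text gives any of these a part in Pass/Fail.

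**The concern.** An exclusion is harmless when it is unrelated to outcome. This one is not. Therapy given between the two Test System shocks normally means that the first has visibly failed, in an open-label study. The subject fits the denominator wording (a Test System shock was delivered) and does not fit the success definition (no Test System shock converted the rhythm), yet leaves the ratio that decides the study.

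The margin is a single failure, so one or two such subjects can settle the result. The study is intended to support a premarket application, and a PP pass would stand even if the planned worst case failed.

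**Working it through.** **Inputs.** 20 subjects (Section 6, Number of Subjects); a 94% point-estimate criterion (Primary Endpoint Analysis); the cut-offs in Table 4. Let N be subjects shocked by the Test System, E those given other therapy before the second shock (early rescue), F those in whom both shocks failed, and C = N − E − F those converted.

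- PP rate = C/(N − E)
- Counted as not converted (worst case among shocked) = C/N
- Best case = (C + E)/N

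**1. Reproduce Table 4.** Two-sided 95% Clopper–Pearson intervals reproduce all eight printed intervals, for example 19/20 (75.1%, 99.9%) and 16/17 (71.3%, 99.9%). The criterion (n − F)/n ≥ 0.94 is F ≤ 0.06n:

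| n | 0.06n | Failures allowed |
|---|---|---|
| 20 | 1.20 | 1 |
| 19 | 1.14 | 1 |
| 18 | 1.08 | 1 |
| 17 | 1.02 | 1 |
| 16 | 0.96 | 0 |

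**2. Consequence.** While N − E is 17 to 20, PP passes exactly when F ≤ 1, and so does the best case. Dropping the subject is therefore equivalent, for the verdict, to a conversion. This covers up to three early rescues if 20 were shocked, two if 19, one if 18 and none if 17. With N = 20:

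| E | F | PP | Counted as not converted | Verdict changes? |
|---|---|---|---|---|
| 1 | 0 | 19/19 = 100%, pass | 19/20 = 95.0%, pass | no |
| 1 | 1 | 18/19 = 94.7%, pass | 18/20 = 90.0%, fail | yes |
| 2 | 0 | 18/18 = 100%, pass | 18/20 = 90.0%, fail | yes |
| 2 | 1 | 17/18 = 94.4%, pass | 17/20 = 85.0%, fail | yes |

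**3. Direction.** C/(N − E) ≥ C/N always, so against scoring the subject as not converted the exclusion can only help. Against the unobserved second-shock result it can hurt. If that shock would have converted, E = 1 and F = 1 give 18/19 = 94.7% under PP and 19/20 = 95.0% with complete data. With N = 17, the same counts give 15/16 = 93.75% (fail) and 16/17 = 94.1% (pass).

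**4. Illustration.** The documents give no rates, so all of these are assumed: first-shock success p1, second-shock success p2, and a share r = 10% of first-shock failures rescued early, independently across 20 shocked subjects. Per subject, e = (1 − p1)r, f = (1 − p1)(1 − r)(1 − p2) and c = 1 − e − f. P(pass) is the exact trinomial sum over outcomes meeting 94%. For complete data, q = (1 − p1)(1 − p2) and P(pass) = (1 − q)^20 + 20q(1 − q)^19.

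For 80%/50%: q = 0.10, so complete P(pass) = 0.1216 + 0.2702 = 0.392. With e = 0.02, f = 0.09 and c = 0.89, PP gives 0.451 and counting as not converted gives 0.338. Shifts in points from complete data, taken before rounding:

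| p1/p2 | Complete | PP | Counted as not converted | P(E ≥ 1) |
|---|---|---|---|---|
| 80/50 | 0.392 | 0.451 (+6.0) | 0.338 (−5.4) | 33% |
| 80/70 | 0.660 | 0.705 (+4.5) | 0.558 (−10.2) | 33% |
| 90/50 | 0.736 | 0.773 (+3.8) | 0.698 (−3.8) | 18% |
| 90/70 | 0.880 | 0.899 (+1.9) | 0.832 (−4.8) | 18% |
| 95/50 | 0.912 | 0.926 (+1.5) | 0.896 (−1.5) | 9.5% |
| 95/70 | 0.964 | 0.971 (+0.6) | 0.948 (−1.6) | 9.5% |

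The 94% rule was also applied when PP n fell below 17, which is outside Table 4; at 10% early rescue this makes no material difference.

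**The case against.** The plan is open about these events. It names them in Table 3, fixes PP exclusions before lock, and requires each occurrence to be reviewed before more subjects are enrolled at that site (text after Table 3; Section 12, Protocol Deviations). It provides training and has CIED therapies off or suspended when the CIED is used for induction. It also schedules ITT, best-case, worst-case and tipping-point analyses, so any conflict with PP will be visible. The sample size is not based on power, and this study is one part of a wider evidence package. Finally, efficacy is cumulative over two shocks and the second result is unobserved, so scoring the subject as a failure is also biased: in the table above its shift equals or exceeds that of PP in five of six scenarios.

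Most of this stands. It limits how often the problem can arise and ensures that it will be seen. It does not alter which analysis decides. Settling exclusions before lock does not help either, because the exclusion follows from an event that occurs after a visible failed shock.

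Three stronger readings are tempting, and the documents do not support them:

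- That the dropped subject is a certain two-shock failure. The second shock was not given, and Table 3 treats the outcome as missing.
- That the exclusion can only favour the device. This is true only against scoring the subject as not converted (step 3).
- That the ITT ratio already counts the subject as a failure. The denominator wording allows that reading, but the missing-data classification points the other way, and the plan does not say how ITT scores the subject.

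**Conclusion.** The point holds in limited form and should be fixed. The exclusion and the equality of verdicts at PP n of 17 to 20 follow from the plan's own text and Table 4 and need no assumption. A single early rescue changes the verdict only when there is exactly one other failure; two or three early rescues among 20 shocked can change it with no other failure.

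The practical size is uncertain because the documents give no early-rescue rate. Under the assumed scenarios PP raises the chance of passing on average, by 0.6 to 6.0 points relative to complete data. These figures illustrate the effect and are not a design property of the study. Nothing here suggests that the plan conceals such events; what is missing is any consequence for the verdict when the worst case fails.

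**What to change.** Keep the PP analysis and add a second condition for a pass: among otherwise eligible, consented subjects who received at least one Test System shock, the worst case must also meet 94%. Alternatively, base Pass/Fail on those subjects and score anyone not converted by a Test System shock as a non-conversion, which follows the plan's own success definition. The two give the same verdict when early rescue is the only deviation, because C/N ≥ 0.94 implies C/(N − E) ≥ 0.94.

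Keep never-shocked subjects, such as those who are non-inducible, out of this denominator; otherwise 18 of 18 shocked and converted would become 18/20 in a worst case over all 20. State how the ITT analysis scores a subject rescued between shocks, report the PP result and best case beside the verdict, and correct the reference from Table 3 to Table 4.

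The cost is protocol and SAP wording, before database lock. The statistical price is conservatism, since some of these subjects might have converted on the second shock: in the scenarios above the rule lowers the chance of passing by about 1.5 to 10.2 points relative to complete data. No change to rescue practice is implied.

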**Table 4: Pass/Fail Criteria - Estimated Conversion Rate Based on Study Results**

Successful Conversion	Estimated Conversion Rate	95% Confidence Interval
20 out of 20	100.0%	(83.2%, 100.0%)
19 out of 20	95.0%	(75.1%, 99.9%)
≤ 18 out of 20	Failure to Meet Primary Endpoint	N/A
19 out of 19	100.0%	(82.4%, 100.0%)
18 out of 19	94.7%	(74.0%, 99.9%)
≤ 17 out of 19	Failure to Meet Primary Endpoint	N/A
18 out of 18	100.0%	(81.5%, 100.0%)
17 out of 18	94.4%	(72.7%, 99.9%)
≤ 16 out of 18	Failure to Meet Primary Endpoint	N/A
17 out of 17	100.0%	(80.5%, 100.0%)
16 out of 17	94.1%	(71.3%, 99.9%)
≤ 15 out of 17	Failure to Meet Primary Endpoint	N/A

Two analyses of the primary endpoint will be conducted, one using the PP data set and a second using the ITT data set. The ITT analysis will include all 20 subjects regardless of missing data. If there is missing data, a tipping point analysis (including best- and worst-case scenarios) will be used to assess sensitivity of the analysis to the missing data. The difference between the conversion rate estimates from the PP and ITT analyses will be used to assess the magnitude of missing data bias.

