### Number of Subjects

This is a fixed study design with 20 subjects.

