**Subject Withdrawals**

Subjects may withdraw from the study for any reason. Subjects may also be removed from the study due to adverse events or Investigator/Sponsor decision. Subjects who are withdrawn from the study will not be replaced.

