### Study Objectives and Endpoints

Efficacy Objective: To evaluate conversion efficacy of the ASSURE WCD Waveform

Primary Endpoint: Estimated cumulative first and second shock VT/VF conversion efficacy  $\geq 94\%$

Secondary Endpoint: First shock conversion efficacy (report only)

Safety Objective: To collect information on adverse events at least possibly related to use of the investigational Test System

Safety Endpoint: Summary of adverse events that are at least possibly related to use of the investigational Test System, including classification of Unanticipated Adverse Device Effects

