### Sample Size Considerations

The sample size set for this study has been scaled to obtain human clinical experience in a comparable number of subjects with attempted shock conversion as reported in the published US LifeVest registry study (Kutyifa V), and account for the potential for missing data (e.g., subjects who fail to have a ventricular arrhythmia induced). The sample size is not power-driven.

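### Subjects with no arrhythmia to treat are classed as missing data together with lost device outcomes, and the plan gives conflicting denominators for subjects who were never shocked

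*Combined protocol and SAP*

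**What the plan says.** **Classification.** Sample Size Considerations (Section 7) says the sample size was chosen partly to "account for the potential for missing data (e.g., subjects who fail to have a ventricular arrhythmia induced". Table 3 opens its list of sources of missing primary-endpoint data with "Unable to induce a ventricular arrhythmia". It then adds a rate that never exceeds 150 bpm, and no attempt because the patient's hemodynamic status changed. The same list holds early rescue shocks, CIED or EP-system therapy given first, setup or operator error, and equipment failure.

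**Who is counted.** Number of Subjects states: "This is a fixed study design with 20 subjects". Under Subject Withdrawals, "Subjects who are withdrawn from the study will not be replaced". Enrollment takes effect when the Test System is connected (Section 9, step 5), before induction (step 7). ITT membership needs only consent and a procedure that was started.

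**Denominator.** Primary Endpoint Analysis divides converted subjects by "the number of total inductions attempted with shocks delivered by the Test System in the respective data set". The text after Table 4 puts all 20 subjects in the ITT analysis whatever is missing, states that where data are missing "a tipping point analysis (including best- and worst-case scenarios) will be used to assess sensitivity of the analysis to the missing data", and reads the gap between the PP and ITT rates as the size of missing-data bias.

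**Decision rule.** Pass/fail compares the PP point estimate with 94%.

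**The concern.** A conversion outcome exists only if there is a qualifying rhythm to convert. A subject who was never induced says nothing about the waveform, and the waveform cannot have caused the non-induction, because it precedes any Test System shock. A subject whose qualifying arrhythmia was ended early by a rescue shock, or who received no shock because the equipment failed, is different: a device outcome was due and was lost.

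The plan puts both kinds in one class and exempts neither from the best- and worst-case analysis. A low worst case could then come from losses that bear on the device or from losses that cannot, and the summary figure would not show which. The PP-to-ITT difference has the same weakness.

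The two denominators go wrong in opposite directions. Counting only inductions with shocks delivered removes non-inductions, but also removes a subject left unshocked by equipment failure, even under ITT. Counting all 20 keeps the equipment failure, but brings in subjects with nothing to convert.

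**Working it through.** **Inputs.** N = 20 (Number of Subjects). Threshold 94% (Study Objectives and Endpoints). Cut-offs and intervals from Table 4. The documents give no non-induction rate, so q is assumed at 2% to 15%. Worst case is taken as missing = failure and best case as missing = success; neither is defined in the plan.

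**1. Reproduce Table 4.** The rate is x/n, with an exact two-sided 95% Clopper-Pearson interval:
- 19/20 = 95.0% (75.1%, 99.9%)
- 18/19 = 94.7% (74.0%, 99.9%)
- 18/18 = 100.0% (81.5%, 100.0%)
- 17/18 = 94.4% (72.7%, 99.9%)

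These match. At n = 20, 19 conversions meet 94% and 18 do not.

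**2. Best and worst case over all 20.** With m subjects missing and f observed failures, worst = (20 − m − f)/20 and best = (20 − f)/20.

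| m | f | Observed | Worst | Best |
|---|---|---|---|---|
| 1 | 0 | 19/19 = 100% | 19/20 = 95% | 20/20 = 100% |
| 2 | 0 | 18/18 = 100% | 18/20 = 90% | 20/20 = 100% |
| 1 | 1 | 18/19 = 94.7% | 18/20 = 90% | 19/20 = 95% |
| 2 | 1 | 17/18 = 94.4% | 17/20 = 85% | 19/20 = 95% |

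In the last three rows the observed rate meets Table 4 and the best case meets 94%; only the worst case falls below it.

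**3. How likely is m ≥ 2 from non-induction alone?** Treating subjects as independent, P(X ≥ 2) = 1 − (1 − q)^20 − 20q(1 − q)^19.
- q = 2%: 6%
- q = 5%: 1 − 0.7358 = 26%
- q = 10%: 1 − 0.3917 = 61%
- q = 15%: 1 − 0.1756 = 82%

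The chance passes one half at q a little above 8%.

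**4. PP versus ITT.** With two non-inductions and every shocked subject converted, PP is 18/18 = 100%. If ITT carries both subjects in the denominator without a success, it is 18/20 = 90%. The plan would read the 10-point gap as missing-data bias, although no device outcome was lost.

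**5. What separating the classes changes.** Take 18 subjects shocked and all converted, plus two others.

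| The two others | All-20 range | Range with only lost outcomes imputed |
|---|---|---|
| Both not induced | 90% to 100% | 18/18 = 100%, nothing to impute |
| One not induced, one lost outcome | 90% to 100% | 18/19 = 94.7% to 19/19 = 100% |
| Both lost outcomes | 90% to 100% | 18/20 = 90% to 20/20 = 100% |

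The all-20 range is the same in each row. With the split, the worst case falls below 94% only in the last row, where two device outcomes really are unknown.

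**The case against.** Several counter-arguments are sound, and they set the limits of the point.

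- **Pass/fail is PP only.** A reader might infer that two non-inductions make the study fail. The documents do not support that: 18/18 and 17/18 both pass, and Table 4 already provides for denominators down to 17.
- **The tipping-point analysis has no success rule.** It reports a range, and nothing in the plan says that a worst case under 94% counts against the device. Missing = failure is itself an inference.
- **One denominator already leaves these subjects out.** Read literally, the Primary Endpoint Analysis ratio excludes anyone never shocked from PP and ITT alike. This is true, but it contradicts the all-20 statement after Table 4, and it would also drop an unshocked equipment failure.
- **Non-induction may be rare.** A history of difficult induction and recent amiodarone use are exclusions, and induction attempts may be repeated. A reader might infer that the sensitivity analysis will usually look fragile. That needs a rate above about 8%, which the documents neither give nor rule out.
- **Reasons are recorded.** The CRF captures the missing-data rationale, so losses could be tabulated by cause. The plan does not say that the sensitivity analysis will use that information.
- **A bound over everyone enrolled is defensible.** Stopping induction and estimating the rate are judgements made in an open-label study, so exclusions on those grounds should not go unexamined. This stands, and is the reason to keep an all-20 line as a supplement.

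**Conclusion.** The point holds as a defect in the ITT and sensitivity analyses, not in the pass/fail decision. The plan gives two incompatible denominators for subjects never shocked, does not define best or worst case, and mixes subjects with nothing to convert with lost device outcomes.

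If missing = failure is what is meant, two non-inductions, or one plus one true failure, bring the all-20 worst case to 90%. In the first case this happens even though every shocked subject converted. The reported missing-data bias could reach 10 points with two non-inductions and no lost outcome. The probability of two or more runs from 6% to 82% over assumed rates of 2% to 15%; how often this would matter therefore cannot be settled from the documents. It is worth correcting because the remedy costs little.

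**What to change.** 1. Reconcile the denominator in Primary Endpoint Analysis with the all-20 ITT statement after Table 4.
2. Split Table 3 into two classes:
   - **A. No qualifying arrhythmia** (not inducible, rate too low, no attempt made): reported by reason in Subject Disposition and kept outside the efficacy denominator.
   - **B. Qualifying arrhythmia present, but the Test System outcome unobserved or pre-empted**, including equipment failure: kept in the ITT denominator and imputed in the main best-case, worst-case and tipping-point analysis.
3. Define best and worst case explicitly, and report the count in each class beside the result. Compute the PP-to-ITT comparison on the same basis.
4. Keep the worst case over all 20 as a labelled supplementary bound.

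The cost is minor SAP wording and one extra table line. Induction attempts, arrhythmia rate, shocks delivered and the missing-data rationale are already on the CRF, so no new data are needed.
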